**Table 8: Operation Characteristics Using Hwang-Shih-DeCani Alpha Spending Function with Shape Parameter -4**

		No. of Subjects (%)	Alpha Spent / Cumulative	Efficacy Boundary or Critical Value (as Compared With Observed Normalized Test Statistic z)
ORR at Day 28	Interim 1	112 (25.7)	–	–
	Interim 2	360 (82.6)	0.0122/0.0122	2.249810
	Final	436 (100)	0.0128/0.025	2.015483

The interim analyses will be performed by an independent statistician and programmer not involved with the conduct of the study as described in the DMC charter.

### 9.2.3. Final Analysis of the Primary Analysis

Final analysis will be conducted when approximately 436 subjects have completed Day 180 or withdrew from the study. If the observed normalized test statistic crosses the efficacy boundary, then superiority of itacitinib plus corticosteroids over placebo plus corticosteroids will be claimed. Again, ORR at Day 28 will be tested first, and if positive, NRM mortality at Day 180 will be tested.

Note that if there is substantial over-running at the end of the study (ie, total number of subjects is greater than 446), the method to adjust the final critical value will be provided in order to control overall Type I error rate. In such a scenario, details in implementation the rules will be specified in the Statistical Analysis Plan.

### 9.3. Level of Significance

The 1-sided significance level for the primary and key secondary endpoint analysis is 0.025. The 2-sided significance level for other analyses is 0.05. All CIs will be 95%.

### 9.4. Statistical Analyses

#### 9.4.1. Primary Analyses

The primary endpoint is ORR at Day 28, defined as the proportion of subjects demonstrating a CR, VGPR, or PR, as per standard criteria (Harris et al 2016, CIBMTR 2009). The comparison of ORR at Day 28 between treatment cohorts will be conducted once the last subject completes the Day 28 visit or withdraws from the study. A CMH test with normal approximation will be used. Summary statistics and 95% CI will be provided.

Subjects who are missing Day 28 aGVHD response assessment data will be considered to be nonresponders.

#### 9.4.2. Secondary Analyses

The key secondary endpoint is NRM at Month 6, defined as the proportion of subjects who died due to causes other than malignancy relapse at Month 6. The comparison of NRM at Month 6 between treatment cohorts will be conducted using a 2-sample proportion test with normal approximation. Summary statistics and 95% CI will be provided.

Additional secondary endpoints will be analyzed as follows:

- ORR, defined as the proportion of subjects demonstrating a CR, VGPR, or PR at Days 14, 56, and 100. The comparison between treatment cohorts will be conducted using a 2-sample proportion test with normal approximation. Summary statistics and applicable 95% CI will be provided.
- NRM, defined as the proportion of subjects who died due to causes other than malignancy relapse at Months 9, 12, and 24. The comparison between treatment cohorts will be conducted using a 2-sample proportion test with normal approximation. Cumulative incidence rates will be provided. Summary statistics and applicable 95% CI will be provided.
- DOR, defined as the time from first response until GVHD progression or death. The comparison between treatment cohorts will be conducted using the log-rank test. The Kaplan-Meier method will be used. Summary statistics will be provided.
- TTR, defined as the interval from treatment initiation to first response.
- Relapse rate of malignant and nonmalignant hematologic diseases, defined as the proportion of subjects whose underlying disease relapses. The comparison between treatment cohorts will be conducted using a 2-sample proportion test with normal approximation. The cumulative incidence rate and summary statistics will be provided.

- Relapse-related mortality rate, defined as the proportion of subjects whose malignancy relapses and has a fatal outcome. The comparison between treatment cohorts will be conducted using a 2-sample proportion test with normal approximation. The cumulative incidence rate and summary statistics will be provided.
- FFS, defined as the proportion of subjects who are still alive, have not relapsed, have not required additional therapy for aGVHD, and have not demonstrated signs or symptoms of cGVHD, at Month 6. The comparison between treatment cohorts will be conducted using the log-rank test. The Kaplan-Meier method will be used. Summary statistics will be provided.
- OS, defined as the time from study enrollment to death due to any cause. The comparison between treatment cohorts will be conducted using the log-rank test. The Kaplan-Meier method will be used. Summary statistics will be provided.
- Clinical safety data (eg, AEs, infections) will be tabulated and listed.
- The plasma PK of itacitinib will be analyzed using a population PK modeling approach.
- Incidence rate of secondary graft failure, defined as > 95% recipient cells any time after engraftment with no signs of relapse, OR retransplantation because of secondary neutropenia ( $< 0.5 \times 10^9/L$ ) and/or thrombocytopenia ( $< 20 \times 10^9/L$ ) within 2 months of transplant.
- Average and cumulative corticosteroid dose at Days 28, 56, 100, and 180.
- Proportion of subjects who discontinue corticosteroids at Days 56 and 100.
- Proportion of subjects who discontinue immunosuppressive medications at Days 56 and 100.
- Incidence rate of aGVHD flares through Day 100.
- Incidence rate of cGVHD (Days 180 and 365 and overall).

[figure not shown]
[REDACTED]

[REDACTED]

Results from the PK [REDACTED] analyses will be performed on the respective populations and summarized at each scheduled visit where the variables are measured.

[REDACTED]

[REDACTED]

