## 2. STUDY OBJECTIVES AND ENDPOINTS

Primary Objective	Primary Endpoint
Compare the efficacy of itacitinib in combination with corticosteroids versus placebo in combination with corticosteroids in terms of ORR at Day 28 in subjects with aGVHD.	ORR at Day 28, defined as the proportion of subjects demonstrating a CR, VGPR, or PR.
Key Secondary Objective	Key Secondary Endpoint
Compare the efficacy between treatment cohorts at a subsequent key clinical landmark.	NRM at Month 6, defined as the proportion of subjects who died due to causes other than malignancy relapse at Month 6.
Secondary Objectives	Secondary Endpoints
Compare additional response and longer-term efficacy outcomes between treatment cohorts.	ORR, defined as the proportion of subjects demonstrating a CR, VGPR, or PR at Days 14, 56, and 100.
	NRM at Months 9, 12, and 24.
	DOR for responders will be calculated. The DoR is defined from the time of the onset of response to loss of response. Subjects who died or discontinued will be censored at the death date or the previous assessment.
	TTR, defined as the interval from treatment initiation to first response.
	Relapse rate of malignant and nonmalignant hematologic diseases, defined as the proportion of subjects whose underlying hematologic disease relapses.
	Malignancy relapse-related mortality rate, defined as the proportion of subjects whose malignancy relapses and has a fatal outcome.
	FFS, defined as the proportion of subjects who are still alive, have not relapsed, have not required additional therapy for aGVHD, and have not demonstrated signs or symptoms of cGVHD, at Month 6.
	OS, defined as the interval from study enrollment to death due to any cause.
Assess the incidence and severity of AEs and SAEs.	Clinical safety data (eg. AEs, infections) will be tabulated and listed.
Evaluate the PK of itacitinib when administered in combination with corticosteroids.	$C_{max}$ , $C_{min}$ , $t_{max}$ , AUC, and CL/F.
Evaluate the incidence of secondary graft failure.	Incidence rate of secondary graft failure, defined as > 95% recipient cells any time after engraftment with no signs of relapse, OR retransplantation because of secondary neutropenia ( $< 0.5 \times 10^9/L$ ) and/or thrombocytopenia ( $< 20 \times 10^9/L$ ) within 2 months of transplant.

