### 9.2. Selection of Sample Size

A sample size of 414 subjects with 1:1 randomization (itacitinib vs placebo) and stratification based on aGVHD risk status (standard risk vs high risk) provides approximately 90% power to test for the primary endpoint (ORR at Day 28) and 83% power to test for the key secondary endpoint (NRM at Month 6). The family-wise  $\alpha$ -level will be controlled at 0.025 overall for the two comparisons. Specifically, this study will claim to have achieved the efficacy objective when the primary endpoint ORR at Day 28 shows a significant treatment effect at 1-sided  $\alpha = 0.025$ . Conditional on significance of the primary endpoint, the key secondary endpoint (NRM at Month 6) will be tested at 1-sided  $\alpha = 0.025$ .

An absolute improvement of 16% in the primary endpoint of ORR at Day 28 would be considered a clinically meaningful improvement over standard first-line systemic treatment for aGVHD (standard care ORR at Day 28:  $P_0 = 0.56$ ; itacitinib ORR at Day 28:  $P_1 = 0.72$ ). A sample size of 414 subjects (207 subjects per treatment arm) will provide approximately 90% power to detect a 16% overall difference (72% vs 56%) between treatment cohorts for the primary endpoint (ORR at Day 28) at a 1-sided alpha level of 0.025. A CMH test with 2-strata will be used.

The assumed Day 28 ORR of 56% is based on MacMillan et al (2015). The stratum-specific response rates (standard risk, 68%; high risk, 44%) assume a standard risk:high risk ratio of 0.50:0.50. It is expected that treatment with itacitinib will result in a 16% increase in the ORR, that is, an expected odds ratio of 2.02 (which corresponds to an overall increase in ORR to 72%), with stratum-specific response rates of 81% and 61% for standard-risk and high-risk aGVHD cohorts, respectively. Power for the CMH test with stratification based on GVHD risk score was calculated using software N-Query 5.0.

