3.2. Control of Type I Error

For the primary and key secondary endpoints, the overall 1-sided Type 1 error is controlled at 0.025. Early stopping for positive efficacy is permitted in this study. Testing of the primary endpoint will use an alpha-spending approach to control Type I error. Subsequent testing of the key secondary endpoint will control Type I error using the Bonferroni method. See Sections 3.4 and 9 for more details.

No multiplicity adjustment will be applied to other endpoints. For estimation purposes, 95% CIs will be provided for parameter estimates of other endpoints.

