7.3.2. Duration of Response for Day 28 Responders

The DOR is defined from the time of the first response to the loss of response (ie, either disease progression or death). Responders who did not progress or die after onset of response will be censored, and response will be ended at either study withdrawal, initiation of new anti-GVHD therapy, or last response assessment before or on the cut-off date, whichever is earliest.

Duration of response will be calculated for every responder as well as Day 28 responders.

The DOR for the Day 28 responders will be assessed using the KM method only for subjects who achieve Day 28 response. The KM curves; medians; 1-, 2-, 6-, 12-, 18- and 24-month (equivalently at Days 30, 60, 180, 365, 547, and 730) survival estimates and 95% CIs will be estimated ([Brookmeyer and Crowley 1982](#)). The DOR will be assessed for each treatment group and also by stratum and Day 28 response status.

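### Protocol 9.4.2 compares duration of response between arms by log-rank in responders only, a group formed after randomisation, so the test can reject in either direction when the drug changes nobody's response duration

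*Protocol*

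**What the plan says.** Protocol Section 2 places DOR under the objective of comparing outcomes between treatment cohorts and limits it to responders: "DOR for responders will be calculated". Protocol 9.4.2 starts the clock at first response, runs it "until GVHD progression or death. The comparison between treatment cohorts will be conducted using the log-rank test", and adds Kaplan-Meier estimation. Protocol 9.3 sets the level: "The 2-sided significance level for other analyses is 0.05". Nothing in the protocol calls this comparison descriptive or brings nonresponders back into it.

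The SAP treats DOR differently. Section 7.3.2 says: "The DOR for the Day 28 responders will be assessed using the KM method only for subjects who achieve Day 28 response". Section 7.3.3 adds two alternative definitions with summary statistics, Kaplan-Meier estimates and plots by arm. Neither section names a between-arm test, whereas SAP 7.4.2, 7.4.9 and 7.4.10 name a stratified log-rank for nonrelapse mortality, failure-free survival and overall survival. SAP 10.1, on changes to protocol-defined analyses, records only that the full analysis set equals the protocol's efficacy evaluable population. SAP 3.2 adds, for endpoints other than the primary and key secondary: "No multiplicity adjustment will be applied to other endpoints".

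**The concern.** A log-rank test of DOR compares placebo responders with itacitinib responders. Randomisation makes the full arms alike, but it does not make the responder subsets alike, because response happens after randomisation and is what the drug is meant to change. Under the plan's own alternative, itacitinib responders consist of subjects who would have responded anyway plus subjects who responded because of the drug. If the two kinds of subject hold a response for different lengths of time, the DOR curves separate even when the drug alters no individual duration. A significant result in either direction could then be read as a drug effect on durability, and a real durability gain could be hidden.

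**Working it through.** **Inputs from the documents.** Protocol 9.2 gives Day 28 response of 68% (standard risk) and 44% (high risk) on placebo, a 50:50 risk mix, and itacitinib "with stratum-specific response rates of 81% and 61% for standard-risk and high-risk aGVHD cohorts, respectively". It plans 207 evaluable and 218 randomised subjects per arm. The DOR test level is two-sided 0.05, so 2.5% in each direction.

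**The plan's own figure.** The plan claims about 90% power to "detect a 16% overall difference (72% vs 56%) between treatment cohorts" with a two-stratum Cochran-Mantel-Haenszel test. With 207/2 = 103.5 subjects per arm per stratum:
- Sum of stratum differences: 0.13 + 0.17 = 0.30.
- Null SE: √[2(0.745×0.255 + 0.525×0.475)/103.5] = 0.0921.
- Alternative SE: √[(0.68×0.32 + 0.81×0.19 + 0.44×0.56 + 0.61×0.39)/103.5] = 0.0909.
- Power: Φ[(0.30 − 1.96×0.0921)/0.0909] = Φ(1.31) = 90.5%. The plan's figure is reproduced.

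**Who enters the DOR comparison**, taking Day 28 response as a stand-in for response at any time:
- Placebo: 218 × 0.56 = 122. Itacitinib: 218 × 0.71 = 155 from the stratum rates, or 218 × 0.72 = 157 from the rounded overall rate.
- If nobody responds on placebo only, added responders make up 0.15/0.71 = 21% (or 0.16/0.72 = 22%) of itacitinib responders.
- High-risk share of responders: 0.44/(0.68 + 0.44) = 39.3% on placebo, and 0.61/(0.81 + 0.61) = 43.0% on itacitinib.

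**Simulation.** There were 4,000 trials per case with 218 per arm, and the drug had no effect on anyone's duration. Assumed, because the documents give no figures: exponential durations, a 180-day median in standard-risk subjects who would respond on either arm, a high-risk hazard of 1, 1.5 or 2 times the standard-risk hazard, and censoring uniform over 180 to 730 days. The 180-day median lies between the Phase 1 medians of 166 and 189.5 days in Protocol 1.4.2. The hazard ratio (HR) compares added responders with subjects who would respond anyway. The table gives the chance of a significant result favouring placebo; each range covers the three high-risk settings.

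| Assumed HR | Unstratified log-rank | Stratified by risk |
|---|---|---|
| 1 | 2.7–3.2% | 2.2–2.9% |
| 1.5 | 7.8–10.0% | 7.5–8.7% |
| 2 | 15.0–16.8% | 15.5–16.1% |
| 3 | 25.2–27.0% | 24.4–26.0% |

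From HR 1.5 upward, unstratified results favouring itacitinib occur in at most 0.5% of trials. At HR 0.67 the bias reverses: 9.5% falsely favour itacitinib when both risk groups share the same hazard, and about 6 to 10% across duration assumptions.

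**Check by formula at HR 2, equal risk hazards.** The itacitinib responder hazard starts at 0.79×1 + 0.21×2 = 1.21 times the placebo one and falls as added responders lose response; the simulated average is 1.14. With 224 events, the expected z is ln(1.1375) × √[224 × (122/277) × (155/277)] = 0.129 × 7.43 = 0.96. Then 1 − Φ(1.96 − 0.96) is about 16%, in line with the simulated 15.0%.

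**Masking.** If the drug truly lowers everyone's hazard of losing response to 0.80, power is 37.6% when added responders are like the others and 9.7% when their HR is 2.

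**The case against.** The strongest reply is that the test may never be run. The SAP (Amendment 1, 23 July 2019) is later than the protocol version it is based on. It gives DOR only Kaplan-Meier estimates and summaries, and its log-rank template in Appendix A uses overall survival as the example. The silence of SAP 10.1 proves little, since it also omits the change of the Month 6 nonrelapse mortality test from a two-sample proportion test to a stratified Cochran-Mantel-Haenszel test. This stands. The documents show a protocol test that was not withdrawn, not one that is certain to be reported. The readable part of the SAP's table list does not reach the DOR tables, so it cannot settle the matter.

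A reader might also infer that the bias must run against itacitinib, and grow with the drug's success. The documents do not support that. Protocol 1.1 says severe disease responds less to steroids and has poorer survival, and Protocol 1.4.3 says Day 28 response predicts later nonrelapse mortality. This makes shorter responses in added responders plausible, but no figure is given: at HR 1 there is no material bias, and below 1 it reverses.

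Nor is the missing stratification the cause. Stratifying by risk leaves the error rate at about 16% at HR 2, and the risk imbalance alone brings it only to 3.2% when high risk doubles the hazard.

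Finally, Protocol 9.4.2 counts any first response, while the rates used here are Day 28 rates. The size is therefore illustrative.

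**Conclusion.** The point holds in a limited form. The protocol's log-rank for DOR is not a randomised comparison, and under the plan's own response rates it can reject with no effect on any subject's duration. Against itacitinib the error is about 8 to 10% at an assumed HR of 1.5 and 15 to 17% at 2, against 2.5% nominal; in its favour, about 6 to 10% at 0.67. These figures rest on the assumed hazard ratios and durations, on Day 28 rates standing in for response at any time, and on nobody responding on placebo only.

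The secure finding is an invalid comparison left standing in the protocol and not reconciled with the SAP. A reader might infer a threat to the trial's main conclusions; there is none, because DOR lies outside the controlled tests of Day 28 response and Month 6 nonrelapse mortality. Low priority.

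**What to change.** - In Protocol 9.4.2, delete the between-arm log-rank for DOR.
- State there and in SAP 7.3.2 and 7.3.3 that DOR in responders is descriptive by arm: Kaplan-Meier estimates with confidence intervals and no p-value.
- Record the change in SAP 10.1.
- Rest any between-arm statement on durability on analyses of all randomised subjects that the SAP already plans: failure-free survival (7.4.9) and response at Days 56, 100 and 180 (7.4.4).

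Mean time in response with nonresponders set to zero should not be added as a durability test, because it mainly reflects the difference in response rate. In simulation it favours itacitinib in 70 to 81% of trials when no one's duration changes, and still in 30 to 58% when every response is truly shortened (hazard × 1.3).

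The cost is a few sentences of wording. No new data, visits or derived variables are needed. What is given up is a DOR p-value that could not be interpreted as a drug effect on durability.

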#### **9.4.4. Safety Analyses**

##### **9.4.4.1. Adverse Events**

A TEAE is either an AE reported for the first time or worsening of a pre-existing condition after first dose of study drug. Analysis of AEs will be limited to TEAEs, but data listings will include all AEs, regardless of their timing to study drug administration. Adverse events will be tabulated by the MedDRA preferred term and system organ class. Severity of AEs will be based on NCI CTCAE v4.03 (NCI 2009).

The subset of AEs considered by the investigator to have a relationship to study drug will be considered to be treatment-related AEs. If the investigator does not specify the relationship of the AE to study drug, the AE will be considered treatment-related. The incidence of AEs and treatment-related AEs will be tabulated.

##### **9.4.4.2. Clinical Laboratory Tests**

Laboratory test values outside the normal range will be assessed for severity based on the normal ranges for the clinical reference laboratory. The incidence of abnormal laboratory values and shift tables relative to baseline will be tabulated.

Laboratory data will be classified into CTC grades for AEs (CTCAE v4.03). The following summaries will be produced for the laboratory data:

- Number and percentage of subjects with worst postbaseline CTC grade (regardless of baseline value). Each subject will be counted only for the worst grade observed postbaseline.
- Shift tables using CTC grades to compare baseline with the worst postbaseline value will be produced with CTC grade.
- For laboratory parameters where CTC grades are not defined, shift tables to the worst postbaseline value will be produced using the low/normal/high classifications based on laboratory reference ranges.

##### **9.4.4.3. Vital Signs**

Descriptive statistics and mean change from baseline will be determined for vital signs (blood pressure, pulse, respiratory rate, and body temperature) at each assessment time. Vital sign results will be reviewed for clinically notable abnormalities (see [Table 9](#)), and subjects exhibiting clinically notable vital sign abnormalities will be listed. A value will be considered an "alert" value if it is outside the established range and shows a > 25% change from baseline.

**Table 9: Criteria for Clinically Notable Vital Sign Abnormalities**

Parameter	High Threshold	Low Threshold
Systolic blood pressure	> 155 mmHg	< 85 mmHg
Diastolic blood pressure	> 100 mmHg	< 40 mmHg
Pulse	> 100 bpm	< 45 bpm
Temperature	> 38°C	< 35.5°C
Respiratory rate	> 24/min	< 8/min

**9.4.4.4. Electrocardiograms**

Electrocardiogram results will be reviewed for clinically notable abnormalities according to predefined criteria (Table 10). Subjects exhibiting clinically notable ECG abnormalities will be listed. Adverse events will be reported for clinically notable abnormalities that are considered clinically significant in the judgment of the investigator.

**Table 10: Criteria for Clinically Notable ECG Abnormalities**

Parameter	High Threshold	Low Threshold
QTcF	> 460 msec	< 295 msec
PR	> 220 msec	< 75 msec
QRS	> 120 msec	< 50 msec
QT	> 500 msec	< 300 msec
RR	> 1330 msec	< 600 msec

QTcF = Fridericia correction.

**9.4.5. Pharmacokinetic Analysis**

A population PK analysis for itacitinib will be performed. The data from this study will be combined with data from Study INCB 39110-108, a Phase 1 study assessing the safety and tolerability of itacitinib in subjects with Grade IIB to IVD aGVHD. Pharmacokinetics data from other clinical studies of itacitinib will also be combined to aid in identification of the structural model, improve parameter estimation, and increase the number of patients with a particular covariate, for example, renal or hepatic impairment, if deemed appropriate.

The population PK data preparation will be performed using SAS version 9.1 or later (SAS Institute Inc., Cary, NC).

[REDACTED]. The PK analyses will use NONMEM version 7.1.0 or later (ICON Development Solutions, Dublin, Ireland).

The individual post hoc PK model parameters (CL/F, V/F, Ka, if applicable) will be determined and will be used to simulate individual exposures. Observed PK parameters such as Cmax, tmax, and Cmin will also be presented and summarized.

Simulation may be used to evaluate potential dose modifications if any covariates, for example, renal or hepatic impairment, are noted to have a clinically significant impact on exposure.

[REDACTED]

